APPENDIX IV-B: THERAPY DELIVERY MAP FOR CYCLE 1, DOSE LEVEL -1

Therapy Delivery Map – Cycle 1, Dose Level -1 This Therapy Delivery Map (TDM) relates to Cycle 1. Each cycle lasts 29 days.	Patient COG ID number _____ DOB _____
---	--

Criteria to start each cycle are in [Section 5.2](#). Extensive treatment details are in [Section 5.1](#).

This TDM is on 4 pages. Flotetuzumab therapy ends on Day 29 given continuous infusion administration.

DRUG	ROUTE	DOSAGE		DAYS	IMPORTANT NOTES
IT Cytarabine (ARAC) (all patients)	Intrathecal (IT)	Age-based dosing: Age (yrs) Dose < 1 20 mg 1-1.99 30 mg 2-2.99 50 mg ≥ 3 70 mg		-6 to 0	Patients should receive a single dose of IT cytarabine administered prior to the start of protocol therapy.
Flotetuzumab	Intravenous (IV)	Day Dose 1 30 nanograms/kg/day 2-3 60 nanograms/kg/day 4-5 100 nanograms/kg/day 6-7 200 nanograms/kg/day 8-28 300 nanograms/kg/day		1 – 28	See Section 5.1 for premedications recommendations. See Section 6 for dose modifications for adverse events.

Ht _____ cm

Wt _____ kg

BSA _____ m²

Dose Level _____ nanograms/kg/day

Date Due	Date Given	Day	IT ARAC _____ mg	Flotetuzumab 30 nanograms/kg/ day ng	Flotetuzumab 60 nanograms/kg/ day ng	Flotetuzumab 100 nanograms/kg/day ng	Flotetuzumab 200 nanograms/kg/day ng	Flotetuzumab 300 nanograms/kg/day ng	Studies
Enter calculated dose above and actual dose administered below									
		Pre-	_____ mg	_____ ng	_____ ng	_____ ng	_____ ng	_____ ng	a – d, f – q, u – x
		1	_____ mg	_____ ng	_____ ng	_____ ng	_____ ng	_____ ng	e, r a, b,

THIS PROTOCOL IS FOR RESEARCH PURPOSES ONLY, SEE PAGE 1 FOR USAGE POLICY

									- t	d, f, g
	2			ng						
	3			ng						
	4				ng				e	
	5				ng					
	6					ng			e	
	7					ng				
	8						ng	e, r, s		
	9						ng	e		
	10						ng			
	11						ng			
	12						ng			
	13						ng	e		
	14						ng			
	15						ng	r		
	16						ng			
	17						ng	e		
	18						ng			
	19						ng			
	20						ng			
	21						ng	e		
	22						ng	r		
	23						ng			
	24						ng			
	25						ng	e		
	26						ng			
	27						ng			
	28						ng			
	29									e, i, j, q, r, v, w, y

THIS PROTOCOL IS FOR RESEARCH PURPOSES ONLY, SEE PAGE 1 FOR USAGE POLICY

Required Observations in Cycle 1**All baseline studies must be performed prior to starting protocol therapy unless otherwise indicated below.**

- a. History. Prior to Cycle 1 and every week during Cycle 1.
- b. Physical exam (including VS). Prior to Cycle 1 and every week during Cycle 1.
- c. Performance Status. Prior to Cycle 1.
- d. CBC/diff/platelets. Prior to Cycle 1 and twice weekly during Cycle 1. If patients have Grade 4 neutropenia then CBCs should be checked at least every other day until recovery to Grade 3 or until meeting the criteria for dose limiting toxicity.
- e. Pharmacokinetics. Samples to be collected from all patients on Cycle 1, Day 1 (pre-infusion), Days 4, 6, and 8 (30 minutes prior to syringe change and dose escalation), Day 9 (24 hours after Day 8 syringe change and final dose escalation) and Days 13, 17, 21, 25, and 29 (at any time) if patient follows the dosing schedule exactly as outlined in [Section 5.1](#). For patients that require dose interruptions during Cycle 1, PK samples should be drawn according to when the patient reaches certain dose levels (see [Appendix VI-B](#) for details). Blood samples will also be collected 30 minutes, 1 hour, 2 hours, 4 hours, 8 hours, and 24 hours after the end of infusion on the patient's last day of protocol therapy. See [Section 8.2](#) for details.
- f. Electrolytes including Ca⁺⁺. Prior to Cycle 1, twice weekly (every 3 to 4 days) during Week 1 of Cycle 1, and then weekly for the duration of Cycle 1.
- g. Creatinine, ALT, bilirubin, and AST. Prior to Cycle 1 and weekly during Cycle 1.
- h. Albumin. Prior to Cycle 1.
- i. Imaging (CT or MRI) of chloroma. Only to be performed if clinically indicated. Prior to Cycle 1 and at the end of Cycle 1 (if present at baseline).
- j. Bone marrow aspirate. Prior to Cycle 1 and at the end of Cycle 1.
- k. Urinalysis. Prior to Cycle 1.
- l. Pregnancy test. Prior to Cycle 1 for women of childbearing potential.
- m. ECHO or gated radionuclide study. Prior to Cycle 1.
- n. EKG. Prior to Cycle 1.
- o. Neurologic exam. Prior to Cycle 1.
- p. Ht/Wt/BSA. Prior to Cycle 1.
- q. NGS MRD comparison with flow cytometry MRD. In consenting patients only at the time of bone marrow evaluation. See [Section 8.5](#) for details.
- r. CD3 T-lymphocyte quantification. In consenting patients, blood samples will be collected on Cycle 1 Days 1, 8, 15, 22, and 29. See [Section 8.6](#) for details.

THIS PROTOCOL IS FOR RESEARCH PURPOSES ONLY, SEE PAGE 1 FOR USAGE POLICY

- s. Cytokine production measurement. In consenting patients, blood samples will be collected on Cycle 1, Day 1 (prior to flotetuzumab infusion) and on Cycle 1, Day 8. Additionally, if patients experience IRR/CRS, blood samples will be collected from consenting patients at the time of IRR/CRS and at the time of IRR/CRS resolution. See [Section 8.7](#) for details.
- t. Immunogenicity study. One sample to be collected from all patients on Cycle 1, Day 1 (pre-infusion). See [Section 8.3](#) for details.
- u. Tumor microenvironment profiling. Prior to Cycle 1. See [Section 8.8](#) for details.
- v. Clot section/biopsy. Prior to Cycle 1 and at the end of Cycle 1. To be performed in conjunction with the bone marrow aspiration.
- w. CD123 site density analysis. In consenting patients prior to Cycle 1. To be performed on the collected bone marrow aspirate. See [Section 8.4](#) for details.
- x. Cytogenetics and FISH. Prior to Cycle 1. To be performed on the collected bone marrow aspirate. It is recommended that cytogenetics/FISH be performed by a COG-approved laboratory.
- y. Flow cytometry with MRD determination. At the end of Cycle 1 with bone marrow evaluation.

This listing only includes evaluations necessary to answer the primary and secondary aims. OBTAIN OTHER STUDIES AS REQUIRED FOR GOOD CLINICAL CARE.

Comments

(Include any held doses, or dose modifications)

THIS PROTOCOL IS FOR RESEARCH PURPOSES ONLY, SEE PAGE 1 FOR USAGE POLICY

APPENDIX IV-C: THERAPY DELIVERY MAP FOR CYCLE 1, DOSE LEVEL 2

Therapy Delivery Map – Cycle 1, Dose Level 2 This Therapy Delivery Map (TDM) relates to Cycle 1. Each cycle lasts 29 days.	Patient COG ID number _____ DOB _____
--	--

Criteria to start each cycle are in [Section 5.2](#). Extensive treatment details are in [Section 5.1](#).

This TDM is on 4 pages. Flotetuzumab therapy ends on Day 29 given continuous infusion administration.

DRUG	ROUTE	DOSAGE		DAYS	IMPORTANT NOTES
IT Cytarabine (ARAC) (all patients)	Intrathecal (IT)	Age-based dosing: Age (yrs) Dose < 1 20 mg 1-1.99 30 mg 2-2.99 50 mg ≥ 3 70 mg		-6 to 0	Patients should receive a single dose of IT cytarabine administered prior to the start of protocol therapy.
Flotetuzumab	Intravenous (IV)	Day	Dose	1 – 28	See Section 5.1 for premedications recommendations. See Section 6 for dose modifications for adverse events.
		1	30 nanograms/kg/day		
		2	100 nanograms/kg/day		
		3	200 nanograms/kg/day		
		4	300 nanograms/kg/day		
		5	400 nanograms/kg/day		
		6	500 nanograms/kg/day		
		7	600 nanograms/kg/day		
		8-28	700 nanograms/kg/day		

THIS PROTOCOL IS FOR RESEARCH PURPOSES ONLY, SEE PAGE 1 FOR USAGE POLICY

Ht _____ cm

Wt _____ kg

BSA _____ m²

Dose Level _____ nanograms/kg/day

Date Due	Date Given	Day	IT ARAC _____ mg	Flotetuzumab 30 nanograms/kg/ day ng	Flotetuzumab 100 nanograms/kg/ day ng	Flotetuzumab 200 nanograms/kg/ day ng	Flotetuzumab 300 nanograms/kg/ day ng	Flotetuzumab 400 nanograms/kg/ day ng	Flotetuzumab 500 nanograms/kg/ day ng	Flotetuzumab 600 nanograms/kg/ day ng	Flotetuzumab 700 nanograms/kg/ day ng	Studies
Enter calculated dose above and actual dose administered below												
		Pre-	_____ mg									a – d, f – q, u – x
		1		_____ ng								r – t
		2			_____ ng							
		3				_____ ng						e
		4					_____ ng					e
		5						_____ ng				e
		6							_____ ng			e
		7								_____ ng		e
		8									_____ ng	e, r, s
		9									_____ ng	e
		10									_____ ng	
		11									_____ ng	
		12									_____ ng	
		13									_____ ng	e
		14									_____ ng	
		15									_____ ng	r
		16									_____ ng	
		17									_____ ng	e
		18									_____ ng	
		19									_____ ng	
		20									_____ ng	
		21									_____ ng	e
		22									_____ ng	r
		23									_____ ng	
		24									_____ ng	
		25									_____ ng	e
		26									_____ ng	
		27									_____ ng	
		28									_____ ng	
		29										e, i, j, q, r, v, w, y

THIS PROTOCOL IS FOR RESEARCH PURPOSES ONLY, SEE PAGE 1 FOR USAGE POLICY

Required Observations in Cycle 1**All baseline studies must be performed prior to starting protocol therapy unless otherwise indicated below.**

- a. History. Prior to Cycle 1 and every week during Cycle 1.
- b. Physical exam (including VS). Prior to Cycle 1 and every week during Cycle 1.
- c. Performance Status. Prior to Cycle 1.
- d. CBC/diff/platelets. Prior to Cycle 1 and twice weekly during Cycle 1. If patients have Grade 4 neutropenia then CBCs should be checked at least every other day until recovery to Grade 3 or until meeting the criteria for dose limiting toxicity.
- e. Pharmacokinetics. Samples to be collected from all patients on Cycle 1, Day 1 (pre-infusion), Days 3 – 8 (30 minutes prior to syringe change and dose escalation), Day 9 (24 hours after Day 8 syringe change and final dose escalation) and Days 13, 17, 21, 25, and 29 (at any time) if patient follows the dosing schedule exactly as outlined in [Section 5.1](#). For patients that require dose interruptions during Cycle 1, PK samples should be drawn according to when the patient reaches certain dose levels (see [Appendix VI-C](#) for details). Blood samples will also be collected 30 minutes, 1 hour, 2 hours, 4 hours, 8 hours, and 24 hours after the end of infusion on the patient's last day of protocol therapy. See [Section 8.2](#) for details.
- f. Electrolytes including Ca⁺⁺. Prior to Cycle 1, twice weekly (every 3 to 4 days) during Week 1 of Cycle 1, and then weekly for the duration of Cycle 1.
- g. Creatinine, ALT, bilirubin, and AST. Prior to Cycle 1 and weekly during Cycle 1.
- h. Albumin. Prior to Cycle 1.
- i. Imaging (CT or MRI) of chloroma. Only to be performed if clinically indicated. Prior to Cycle 1 and at the end of Cycle 1 (if present at baseline).
- j. Bone marrow aspirate. Prior to Cycle 1 and at the end of Cycle 1.
- k. Urinalysis. Prior to Cycle 1.
- l. Pregnancy test. Prior to Cycle 1 for women of childbearing potential.
- m. ECHO or gated radionuclide study. Prior to Cycle 1.
- n. EKG. Prior to Cycle 1.
- o. Neurologic exam. Prior to Cycle 1.
- p. Ht/Wt/BSA. Prior to Cycle 1.
- q. NGS MRD comparison with flow cytometry MRD. In consenting patients only at the time of bone marrow evaluation. See [Section 8.5](#) for details.
- r. CD3 T-lymphocyte quantification. In consenting patients, blood samples will be collected on Cycle 1 Days 1, 8, 15, 22, and 29. See [Section 8.6](#) for details.

THIS PROTOCOL IS FOR RESEARCH PURPOSES ONLY, SEE PAGE 1 FOR USAGE POLICY

- s. Cytokine production measurement. In consenting patients, blood samples will be collected on Cycle 1, Day 1 (prior to flotetuzumab infusion) and on Cycle 1, Day 8. Additionally, if patients experience IRR/CRS, blood samples will be collected from consenting patients at the time of IRR/CRS and at the time of IRR/CRS resolution. See [Section 8.7](#) for details.
- t. Immunogenicity study. One sample to be collected from all patients on Cycle 1, Day 1 (pre-infusion). See [Section 8.3](#) for details.
- u. Tumor microenvironment profiling. Prior to Cycle 1. See [Section 8.8](#) for details.
- v. Clot section/biopsy. Prior to Cycle 1 and at the end of Cycle 1. To be performed in conjunction with the bone marrow aspiration.
- w. CD123 site density analysis. In consenting patients prior to Cycle 1. To be performed on the collected bone marrow aspirate. See [Section 8.4](#) for details.
- x. Cytogenetics and FISH. Prior to Cycle 1. To be performed on the collected bone marrow aspirate. It is recommended that cytogenetics/FISH be performed by a COG-approved laboratory.
- y. Flow cytometry with MRD determination. At the end of Cycle 1 with bone marrow evaluation.

This listing only includes evaluations necessary to answer the primary and secondary aims. OBTAIN OTHER STUDIES AS REQUIRED FOR GOOD CLINICAL CARE.

Comments

(Include any held doses, or dose modifications)

THIS PROTOCOL IS FOR RESEARCH PURPOSES ONLY, SEE PAGE 1 FOR USAGE POLICY

APPENDIX V: THERAPY DELIVERY MAP FOR CYCLES 2+

Therapy Delivery Map – Cycles 2+ This Therapy Delivery Map (TDM) relates to Cycles 2+. Each cycle lasts 29 days.	Patient COG ID number DOB
--	------------------------------

Criteria to start each cycle are in [Section 5.2](#). Extensive treatment details are in [Section 5.1](#).

This TDM is on 4 pages. Flotetuzumab therapy ends on Day 29 given continuous infusion administration.

DRUG	ROUTE	DOSAGE	DAYS	IMPORTANT NOTES										
IT Cytarabine (ARAC) (all patients)	Intrathecal (IT)	Age-based dosing: 

Age (yrs)	Dose	

< 1	20 mg	

1-1.99	30 mg	

2-2.99	50 mg	

≥ 3	70 mg	

	Age (yrs)	Dose	< 1	20 mg	1-1.99	30 mg	2-2.99	50 mg	≥ 3	70 mg	1	Subsequent doses and timing may be administered at the discretion of the treating physician.
Age (yrs)	Dose													
< 1	20 mg													
1-1.99	30 mg													
2-2.99	50 mg													
≥ 3	70 mg													
Flotetuzumab	Intravenous (IV)	At Cycle 1 target dose	1-28	See Section 5.1 for premedications recommendations. See Section 6 for dose modifications for adverse events.										

NOTE: If a treatment-free interval > 3 days occurs between any 2 cycles, the subsequent cycle will require step-up dosing. If a treatment-free interval > 3 days occurs between any 2 cycles, the Study Chair must be notified and the subsequent cycle dosing schedule must be discussed.

THIS PROTOCOL IS FOR RESEARCH PURPOSES ONLY, SEE PAGE 1 FOR USAGE POLICY

Ht _____ cm Wt _____ kg BSA _____ m² Dose Level _____ nanograms/kg/day

Date Due	Date Given	Day	IT ARAC _____ mg	Flotetuzumab at Cycle 1 Target Dose nanograms/kg/ day	Studies
Enter calculated dose above and actual dose administered below					
		Pre-			a, b, d - g, i - k, m
		1	_____ mg	_____ ng	1, o
		2		_____ ng	
		3		_____ ng	
		4		_____ ng	
		5		_____ ng	
		6		_____ ng	
		7		_____ ng	
		8		_____ ng	
		9		_____ ng	
		10		_____ ng	
		11		_____ ng	
		12		_____ ng	
		13		_____ ng	
		14		_____ ng	
		15		_____ ng	
		16		_____ ng	
		17		_____ ng	
		18		_____ ng	
		19		_____ ng	
		20		_____ ng	
		21		_____ ng	
		22		_____ ng	
		23		_____ ng	c

THIS PROTOCOL IS FOR RESEARCH PURPOSES ONLY, SEE PAGE 1 FOR USAGE POLICY

	24		ng		
	25		ng		
	26		ng		
	27		ng		
	28		ng		
	29			h, n, p, q, r	

Required Observations for Cycles 2+

- a. History. Prior to subsequent cycles.
- b. Physical exam (including VS). Prior to subsequent cycles.
- c. CBC/diff/platelets. Weekly. If patients develop Grade 4 neutropenia then CBCs should be checked at least every 3 to 4 days until recovery to Grade 3 or until meeting the criteria for dose limiting toxicity.
- d. Ht/Wt/BSA. Prior to subsequent cycles.
- e. Electrolytes including Ca⁺⁺. Prior to subsequent cycles.
- f. Creatinine, ALT, bilirubin, and AST. Prior to subsequent cycles.
- g. Albumin. Prior to subsequent cycles.
- h. Imaging (CT or MRI) of chloroma. Only to be performed if clinically indicated. At the end of every cycle (if present on previous study).
- i. ECHO or gated radionuclide study. Prior to subsequent cycles.
- j. EKG. Prior to subsequent cycles.
- k. Neurologic exam. Prior to subsequent cycles.
- l. CD3 T-lymphocyte quantification. In consenting patients, samples to be collected on Day 1 of Cycles 2+. See [Section 8.6](#) for details.
- m. Cytokine production measurement. If patients experience IRR/CRS, blood samples are to be collected from consenting patients at the time of IRR/CRS and at the time of IRR/CRS resolution (if applicable). See [Section 8.7](#) for details.
- n. Bone marrow aspirate. At the end of every cycle.
- o. Immunogenicity study. Samples to be collected from all patients on Cycle 3, Day 1 (pre-infusion), and on Cycle 5, Day 1 (pre-infusion). See [Section 8.3](#) for details.
- p. Pharmacokinetics. Blood samples will be collected 30 minutes, 1 hour, 2 hours, 4 hours, 8 hours, and 24 hours after the end of infusion on the patient's last day of

THIS PROTOCOL IS FOR RESEARCH PURPOSES ONLY, SEE PAGE 1 FOR USAGE POLICY

protocol therapy. See [Section 8.2](#) for details.

- q. NGS MRD comparison with flow cytometry MRD. In consenting patients only at the time of bone marrow evaluation. See [Section 8.5](#) for details.
- r. Flow cytometry with MRD determination. At the end of each cycle with bone marrow evaluation.

This listing only includes evaluations necessary to answer the primary and secondary aims. OBTAIN OTHER STUDIES AS REQUIRED FOR GOOD CLINICAL CARE.

Comments

(Include any held doses, or dose modifications)

THIS PROTOCOL IS FOR RESEARCH PURPOSES ONLY, SEE PAGE 1 FOR USAGE POLICY

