6.2 Dose Modifications for Non-Hematological Toxicity

- 6.2.1 Patients who have any dose-limiting non-hematological toxicity (as defined in [Section 5.5.1](#)) may continue on protocol therapy upon meeting eligibility lab requirements or baseline but should receive subsequent doses at the next lower dose level.
- 6.2.2 If a non-hematological dose-limiting toxicity recurs after one dose reduction, the patient must be removed from protocol therapy.
- 6.2.3 Patients who have a dose-limiting non-hematological toxicity that does not resolve to baseline or eligibility within 21 days after the planned start of the next treatment cycle must be removed from protocol therapy.

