8.0 EVALUATIONS/MATERIAL AND DATA TO BE ACCESSIONED

8.1 Required Clinical, Laboratory and Disease Evaluation

All clinical and laboratory studies to determine eligibility must be performed within 7 days

THIS PROTOCOL IS FOR RESEARCH PURPOSES ONLY, SEE PAGE 1 FOR USAGE POLICY

prior to enrollment unless otherwise indicated. Laboratory values used to assess eligibility (see [Section 4.0](#)) must be no older than seven (7) days at the start of therapy. Laboratory tests need **not** be repeated if therapy starts **within** seven (7) days of obtaining labs to assess eligibility. If a post-enrollment lab value is outside the limits of eligibility, or laboratory values are older than 7 days, then the following laboratory evaluations must be re-checked within 48 hours prior to initiating therapy: CBC with differential, bilirubin, ALT (SGPT) and serum creatinine. If the recheck is outside the limits of eligibility, the patient may not receive protocol therapy and will be considered off protocol therapy. Imaging studies, bone marrow aspirate, and biopsy must be obtained within 14 days prior to start of protocol therapy (repeat the imaging if necessary).

STUDIES TO BE OBTAINED	Pre-Study	During Cycle 1	Prior to Subsequent Cycles [^]
History	X	Weekly	X
Physical exam with vital signs	X	Weekly	X
Height, weight, BSA	X		X
Performance status	X		
CBC, differential, platelets	X	Twice Weekly (every 3 to 4 days) ³	Weekly ⁴
Pharmacokinetics		X ¹	X ¹
Anti-drug antibody (ADA)		X ¹⁰	X ¹⁰
Urinalysis	X		
Electrolytes including Ca ⁺⁺	X	Twice weekly (every 3 to 4 days) during Week 1, then weekly	X
Creatinine, ALT, bilirubin, AST	X	Weekly	X
Albumin	X		X
Imaging (CT or MRI) of chloroma (if clinically indicated)	X	End of Cycle 1 (if present at baseline)	End of each cycle (if present on previous study)
Bone marrow aspiration	X ^{5, 6, 12, 13}	End of Cycle 1 ⁵	End of every cycle
Pregnancy test ²	X		
ECHO or gated radionuclide study	X		X
EKG	X		X
Neurologic exam	X		X
Next-generation sequencing (NGS) MRD analysis	With bone marrow evaluation ^{7,13}	With bone marrow evaluation ⁷	With bone marrow evaluation ⁷
Peripheral T cell quantification		X ⁸	X ⁸
Cytokine analysis		X ⁹	X ⁹
Tumor Microenvironment Profiling	X ^{11, 13}		
Flow cytometry with minimal residual disease determination (MRD) ¹⁴		With bone marrow evaluation	With bone marrow evaluation

[^] Studies may be obtained within 72 hours prior to the start of the subsequent cycle.

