4	0	0, 1, 2 or 3	1, 2, 3 or 4	Same dose level
4	1	0, 1, 2 or 3	0, 1, 2 or 3	Same dose level
4	0	4	0	Escalate**
4	≥ 2	0, 1 or 2	0, 1 or 2	De-escalate*
5	0	0, 1, 2, 3 or 4	1, 2, 3, 4 or 5	Same dose level
5	1	0, 1, 2, 3 or 4	0, 1, 2, 3 or 4	Same dose level
5	0	5	0	Escalate**
5	≥ 2	0, 1, 2 or 3	0, 1, 2 or 3	De-escalate*
6	0	0, 1, 2, 3, or 4	2, 3, 4, 5 or 6	Suspend
6	1	0, 1, 2, 3 or 4	0, 1, 2, 3 or 4	Suspend
6	0 or 1	5 or 6	0 or 1	Escalate**
6	≥ 2	0, 1, 2, 3 or 4	0, 1, 2, 3 or 4	De-escalate*

* If six patients already entered at next lower dose level, the MTD has been defined.

** If final dose level has been reached, the recommended dose has been reached.

If two or more of a cohort of up to six patients experience DLT at a given dose level, then the MTD has been exceeded and dose escalation will be stopped (see [Section 11.2.2](#) for exception to rule).

In addition to determination of the MTD, a descriptive summary of all toxicities will be reported.

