13.4 Definition of Onset and Resolution of Adverse Events

Note: These guidelines below are for reporting adverse events on the COG PEP-CTN case report forms and do not alter the guidelines for CTEP-AERS reporting.

- 13.4.1 If an adverse event occurs more than once in a course (cycle) of therapy only the most severe grade of the event should be reported.
- 13.4.2 If an adverse event progresses through several grades during one course of therapy, only the most severe grade should be reported.
- 13.4.3 The duration of the AE is defined as the duration of the highest (most severe) grade of the Adverse Effects.
- 13.4.4 The resolution date of the AE is defined as the date at which the AE returns to baseline or less than or equal to Grade 1, whichever level is higher (note that the resolution date may therefore be different from the date at which the grade of the AE decreased from its highest grade). If the AE does not return to baseline the resolution date should be recorded as "ongoing."
- 13.4.5 An adverse event that persists from one course to another should only be reported once unless the grade becomes more severe in a subsequent course. An adverse event which resolves and then recurs during a different course, must be reported each course it recurs.

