		3				_____ ng					d, f, g
		4					_____ ng				e
		5						_____ ng			e
		6							_____ ng		e
		7								_____ ng	e
		8								_____ ng	e, r, s
		9								_____ ng	a, b,
		10								_____ ng	d,
		11								_____ ng	f, g
		12								_____ ng	e
		13								_____ ng	
		14								_____ ng	
		15								_____ ng	r, e
		16								_____ ng	a,
		17								_____ ng	b,
		18								_____ ng	d,
		19								_____ ng	f,
		20								_____ ng	g
		21								_____ ng	
		22								_____ ng	e, r
		23								_____ ng	a, b,
		24								_____ ng	d,

THIS PROTOCOL IS FOR RESEARCH PURPOSES ONLY, SEE PAGE 1 FOR USAGE POLICY

		25								ng		f, g
		26								ng		
		27								ng	e	
		28								ng		
		29									e, i, j, q, r, v, w, y	

Required Observations in Cycle 1

All baseline studies must be performed prior to starting protocol therapy unless otherwise indicated below.

- a. History. Prior to Cycle 1 and every week during Cycle 1.
- b. Physical exam (including VS). Prior to Cycle 1 and every week during Cycle 1.
- c. Performance Status. Prior to Cycle 1.
- d. CBC/diff/platelets. Prior to Cycle 1 and twice weekly during Cycle 1. If patients have Grade 4 neutropenia then CBCs should be checked at least every other day until recovery to Grade 3 or until meeting the criteria for dose limiting toxicity.
- e. Pharmacokinetics. Samples to be collected from all patients on Cycle 1, Day 1 (pre-infusion), Days 3 – 7 (30 minutes prior to syringe change and dose escalation), Day 8 (24 hours after Day 7 syringe change and final dose escalation), and Days 12, 15, 19, 22, 27, and 29 (at any time) if patient follows the dosing schedule exactly as outlined in [Section 5.1](#). For patients that require dose interruptions during Cycle 1, PK samples should be drawn according to when the patient reaches certain dose levels (see [Appendix VI-A](#) for details). Blood samples will also be collected 30 minutes, 1 hour, 2 hours, 4 hours, 8 hours, and 24 hours after the end of infusion on the patient's last day of protocol therapy. See [Section 8.2](#) for details.
- f. Electrolytes including Ca⁺⁺. Prior to Cycle 1, twice weekly (every 3 to 4 days) during Week 1 of Cycle 1, and then weekly for the duration of Cycle 1.
- g. Creatinine, ALT, bilirubin, and AST. Prior to Cycle 1 and weekly during Cycle 1.
- h. Albumin. Prior to Cycle 1.
- i. Imaging (CT or MRI) of chloroma. Only to be performed if clinically indicated. Prior to Cycle 1 and at the end of Cycle 1 (if present at baseline).

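### From Cycle 2 on, chemistry and exams are scheduled only before the next cycle, with no end-of-therapy set, so a last cycle in Cycles 2–6 has none scheduled after it starts

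*Combined protocol and SAP*

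**What the plan says.** **Cycle 1.** Appendices IV-A to IV-C, matching Section 8.1, schedule "Creatinine, ALT, bilirubin, and AST. Prior to Cycle 1 and weekly during Cycle 1". History and exam are also weekly. Electrolytes are twice weekly in Week 1 and weekly after that. CBC is twice weekly. ECHO, EKG, neurologic exam and albumin are baseline only.

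**Cycles 2+.** Appendix V has "Creatinine, ALT, bilirubin, and AST. Prior to subsequent cycles", "Physical exam (including VS). Prior to subsequent cycles" and "ECHO or gated radionuclide study. Prior to subsequent cycles". History, electrolytes, albumin, EKG and neurologic exam have the same timing. On the therapy delivery map these items sit in the pre-cycle row. Day 29 carries only chloroma imaging, marrow, PK and the two minimal residual disease items. The CBC is the only one of these safety tests that stays weekly.

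**Timing.** The footnote to the Section 8.1 table says "Studies may be obtained within 72 hours prior to the start of the subsequent cycle". The pre-cycle tests therefore double as the end-of-cycle check on the cycle just finished, provided another cycle is planned.

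**After removal.** Section 10.1 keeps the Section 8.1 observations going for patients removed during Cycle 1. Patients removed later get only what clinical care requires.

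**Use of the data.** Under Section 11.3, "a descriptive summary of all toxicities will be reported". Section 13.4.5 records events by course: "An adverse event which resolves and then recurs during a different course, must be reported each course it recurs". Section 6.2.2 applies DLT-type definitions in later cycles: "If a non-hematological dose-limiting toxicity recurs after one dose reduction, the patient must be removed from protocol therapy".

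**The concern.** Safety and tolerability is primary aim 1.1.1 and is not confined to Cycle 1. A raised ALT or creatinine without symptoms becomes an adverse event only when someone draws blood. If the draw depends on a further cycle being planned, the last treated cycle is the least observed. Section 5.1 allows later cycles as an outpatient, so incidental inpatient testing cannot be relied on.

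Sparse testing also weakens the grading rules. Section 5.5.1 depends on whether liver enzymes recover within 7 days and electrolytes within 72 hours, and Sections 13.4.3 and 13.4.4 ask for duration and resolution dates. One scheduled test per cycle, or none, cannot supply these. A pooled summary would then mix a closely tested Cycle 1 with thinly tested later cycles, and a reader could take fewer laboratory findings later on as evidence of better tolerance.

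**Working it through.** The plan gives no figure on this point, so there is none to reproduce. The check counts scheduled assessments, derives a bound, and adds an illustration.

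**1. Scheduled assessments after a cycle starts** (Section 8.1, Appendices IV and V)

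| Cycle | Creatinine/ALT/AST/bilirubin | ECHO, EKG, neurologic exam |
|---|---|---|
| Cycle 1 | about 4 (weekly) | 1 if another cycle follows, otherwise 0 |
| Cycles 2–5, another cycle follows | 1 (the next cycle's pre-test) | 1 |
| Last cycle, Cycles 2–6 | 0 | 0 |

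History and exam follow the chemistry column. So do electrolytes, with one extra Week 1 draw in Cycle 1. The drop after Cycle 1 concerns history, exam, chemistry and electrolytes. ECHO, EKG and neurologic exam are no less frequent after Cycle 1 than during it. Their gap is that nothing is scheduled once the final cycle begins, whichever cycle that is.

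**2. Share of later patient-cycles with no chemistry scheduled after the start.** Therapy stops at 6 cycles, so a patient who enters Cycle 2 has between 1 and 5 later cycles (Cycles 2 to 6), exactly one of which is the last. With N such patients:

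share = N / (total Cycle 2+ patient-cycles) ≥ N / (5N) = 1/5 = 20%.

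This bound needs no assumption about response or continuation.

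**3. Illustration: chance that a silent abnormality meets a scheduled test.** Assume onset is uniform over the 28 infusion days and the abnormality lasts d days. Both are assumptions; the documents give neither. Weekly testing gives min(1, d/7), one test near the end of the cycle gives d/28, and no test gives 0.

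| d (days) | Cycle 1, weekly | Cycles 2–5, not last | Last cycle, Cycles 2–6 |
|---|---|---|---|
| 3 | 3/7 = 43% | 3/28 = 11% | 0% |
| 7 | 100% | 7/28 = 25% | 0% |
| 14 | 100% | 14/28 = 50% | 0% |

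**4. Shape across cycles.** Take d = 14, and assume that 22–60% of patients continue after Cycle 2 and 50–90% after each of Cycles 3–5. Detection averaged over patients is the share continuing × 14/28:

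- Cycle 1: 100%
- Cycle 2: 0.22 × 0.5 to 0.60 × 0.5 = 11–30%
- Cycles 3–5: 0.50 × 0.5 to 0.90 × 0.5 = 25–45%
- Cycle 6: 0%

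This is a step down after Cycle 1 plus a last-cycle gap. It is not a steady fall, since Cycle 2 is lower than Cycles 3–5.

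**5. Effect of one end-of-therapy set.** A draw 24 h after the infusion ends detects an onset during the infusion with probability (d − 1)/28. That is 2/28 = 7%, 6/28 = 21% and 13/28 = 46% for d = 3, 7 and 14, against 0% now.

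**The case against.** The strongest reply is that much safety observation continues. CBC stays weekly. Adverse events are reported at the end of every cycle (Section 13.5.1), and those present or emerging within 30 days of the last dose must be followed and reported (Section 10.1). Appendix V tells sites to obtain other studies needed for good care. This stands for symptomatic events. It does not cover silent laboratory changes, and it leaves their detection to site practice.

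Second, patients may move on while awaiting the marrow result (Section 5.2). Some will have pre-cycle tests drawn for a cycle they never receive. That is correct: zero scheduled tests does not mean zero tests in practice.

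Three stronger readings are tempting, and the documents do not support them.

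- **Recorded toxicity must fall with cycle number.** What falls is scheduled detection of silent findings, in the pattern shown in step 4. No by-cycle comparison is planned.
- **The reduction and removal rules of Section 6.2 cannot operate.** Section 5.2 requires the eligibility laboratory parameters to be met before each further cycle, and clinically detected events also count. After a completed final cycle no further dose is at stake.
- **About half to four-fifths of later cycles are affected.** Taking the adult response share as the share r continuing past Cycle 2, with those patients stopping after Cycle L, the affected share is 1/(1 + r(L − 2)). Section 2.3.1 prints 26% beside 6/27, but 6/27 = 22% and 7/27 = 26%. With r = 0.22–0.26 and L = 3–6, the result is 49–82%. But that r describes all response-evaluable adults, and the formula needs patients who entered Cycle 2. If, as an assumption, half of them entered, r doubles to 0.44–0.52 and the range becomes about 33–69%.

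**Conclusion.** The gap is real, explicit and consistent between Section 8.1 and Appendix V. Silent laboratory toxicity in later cycles can be missed, and laboratory toxicity rates in Cycle 1 and Cycles 2+ are not comparable.

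The firm size is that at least 20% of Cycle 2+ patient-cycles have no chemistry scheduled after they start. Any higher share depends on continuation rates that the documents do not give for this population. The detection percentages are illustrative and depend on the assumed onset and duration.

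The dose decision is not affected, because the DLT window is Cycle 1, where chemistry is at least weekly. A patient whose last cycle is Cycle 1 is covered for chemistry, electrolytes and exam, but not for ECHO, EKG or neurologic exam. The point is a cheap improvement to safety ascertainment for aim 1.1.1, not a flaw in the dose-finding.

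**What to change.** **Section 8.1 and Appendix V:** add one end-of-therapy set of creatinine, ALT, AST, bilirubin and electrolytes, taken with the 24 h post-infusion PK draw that Section 8.2.2 already requires, and a history and exam at the same contact. The sponsor may also consider adding chemistry to the weekly CBC draws in Cycles 2+. An end-of-therapy set alone closes the last-cycle gap but does not restore Cycle 1 frequency.

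**Section 11.3:** tabulate toxicities separately for Cycle 1 and Cycles 2+. Use the number of patients actually tested in that period as the denominator for laboratory, ECHO/EKG and neurologic findings. This adds no ECHO, EKG or neurologic exam, but it shows how few patients were assessed.

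**Cost:** wording in one table and one appendix, a small extra blood volume on an existing draw, and some extra data entry. The tabulation needs no new data. No dose or treatment rule changes.
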